Main criteria for inclusion: Histologically-confirmed locally advanced or metastatic breast cancer not deemed amenable to curative surgery or curative radiation therapy Tumors are positive for estrogen-receptor (ER) and/or progesterone receptor (PgR); HER2 negative Postmenopausal women Disease refractory to non-steroidal aromatase inhibitors Objective evidence of recurrence or progression on or after the last systemic therapy prior to the study entry Patients must have a measurable lesion according to RECIST version 1.1 or bone lesion <del>only</del> : lytic or mixed (lytic + sclerotic) in the absence of measurable lesion				
Test product(s): BI 836845 dose: Phase I: 750 mg weekly as starting dose; Phase II: RP2D as established in Phase I mode of admin.: Intravenous infusion over 60 minutes				
Comparator products: Exemestane plus Everolimus dose: Exemestane: 25 mg per day Everolimus: Phase I: 10 mg per day as starting dose; Phase II: Arm 1: 10 mg per day, Arm 2: RP2D as established in Phase I mode of admin.: Oral				
Duration of treatment: Continuous treatment until disease progression, intolerable AEs, consent withdrawal or non-compliance with the study protocol				

Proprietary confidential information.

© 2016 Boehringer Ingelheim International GmbH or one or more of its affiliated companies. All rights reserved.

This document may not - in full or in part - be passed on, reproduced, published or otherwise used without prior written permission.

Name of company: Boehringer Ingelheim		Tabulated Trial Protocol		
Name of finished product: Not applicable				
Name of active ingredient: BI 836845				
Protocol date: 13 December 2013	Trial number: 1280.4		Revision date: 30 March 2016	
Criteria for efficacy: The primary endpoint of the phase II part of this study is progression-free survival, as determined by RECIST 1.1. Secondary endpoints are: 

• Time to progression

• Objective response (CR, PR)

• Time to objective response

• Duration of objective response

• Disease Control (CR + PR + SD24w + Non-CR/Non-PD24w)

• Duration of disease control

				

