### 3. DESCRIPTION OF DESIGN AND TRIAL POPULATION

#### 3.1 OVERALL TRIAL DESIGN AND PLAN

This clinical trial will involve two components: a dose finding Phase I part followed by a two-arm, open-label, randomized Phase II part. As the steady state of everolimus and exemestane is reached in about 7 days ([R08-5716](#), [R13-0654](#), [R13-0655](#)), to assess the pharmacokinetic and biomarker effect, a run-in treatment with exemestane and everolimus for 7 days prior to commencing the combination therapy with BI 836845 in the Phase I part is mandated. In addition, given the elimination half-life of all study drugs, the (first) follow-up visit is scheduled 42 days after last dose of study drug administration in order to assess the PK, biomarker and immunogenicity of BI 836845 when study drugs have been eliminated from the body.

Patients are included in the study once the informed consent is signed. The screening period will be up to 4 weeks (28 days) during which time the eligibility will be confirmed. The eligibility criteria will be reconfirmed prior to the first administration of study medications, eligible patients will be treated continuously with the study regimen in the absence of disease progression, intolerable adverse events, or other reason necessitating withdrawal (refer to [Section 3.3.4](#)). The treatment will be administered as courses of 28 days. Continued treatment beyond disease progression will not be allowed in the study.

Tumor response and progression will be assessed using RECIST 1.1 ([R09-0262](#)). Assessment at the investigator site will be used to make decisions on eligibility and continuation of treatment.

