### 7.3 PLANNED ANALYSES

During the Phase I part, cohorts of patients treated with BI 836845 in combination with exemestane and everolimus will be evaluated continuously based on the totality of the safety data available in order to determine the recommended phase II dose.

Efficacy analysis will include all randomised patients in the Phase II part. For the Phase I dose finding stage, PFS and objective tumor response will be summarized descriptively by cohort. No comparison will be done between cohorts.

Safety analysis will be summarized separately for patients treated in the Phase I and Phase II part of the trial. The safety profile of the Phase II part will be compared in a descriptive manner between the experimental and the control arm.

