#### 7.3.1 Primary analyses

The primary analysis of PFS will be conducted and reported when approximately 90 patients (out of 150 randomized patients) have progressed or died. However, it may be performed with fewer events within approximately 30 months after the first patient is randomized in the Phase II part. Any additional information collected after the data cut-off for the primary analysis will be reported in a revised clinical trial report.

The stratified Cox proportional hazards model will be applied to derive the estimate and confidence interval of the hazard ratio between the two treatment arms, stratified by visceral involvement (yes vs. no). Median PFS and PFS rate at certain time points, e.g. 2, 4, 6 months after randomization will be calculated from Kaplan-Meier curves with 95% confidence interval using the Greenwood variance estimate. Nominal p-value of a two-sided log-rank test on PFS will also be provided.

Response and disease progression is assessed according to RECIST 1.1. Refer to [Section 5.1.1.2](#) for PFS definition. Clinical deterioration without image-based progression

Proprietary confidential information.

© 2016 Boehringer Ingelheim International GmbH or one or more of its affiliated companies. All rights reserved.

This document may not - in full or in part - be passed on, reproduced, published or otherwise used without prior written permission.

will be censored from the primary analysis, but will be examined as part of a sensitivity analysis.

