## 7.6 DETERMINATION OF SAMPLE SIZE

The Phase I part follows a 3+3 design to determine the MTD and RP2D of BI 836845 in combination with exemestane and everolimus. A total of 12 patients will be treated at the RP2D level before commencing the Phase II part. Assuming two cohorts are needed with 3 patients treated in the first cohort, at least 15 evaluable patients will be needed to determine the RP2D in the Phase I part.

Once the RP2D is determined, the Phase II part of the study will start.

[figure not shown]
In parallel with the commencing Phase II part, an additional 6 patients will be treated in the setting of the Phase I part of the study on the RP2D (leading to a total number of 18 fully evaluable patients at that level), to investigate [REDACTED]

[REDACTED]. These additional patients are needed to allow for an estimation of a potential impact of BI 836845 on the [REDACTED]

Proprietary confidential information.

© 2016 Boehringer Ingelheim International GmbH or one or more of its affiliated companies. All rights reserved.

This document may not - in full or in part - be passed on, reproduced, published or otherwise used without prior written permission.

The phase II part of the study is intended to provide evidence that will allow informed decision making in terms of the next stages of development. It is therefore sized such that, if the true effect of BI 836845 in combination with exemestane and everolimus relative to exemestane and everolimus alone had a hazard ratio of 0.72 (median PFS 10.8 months of triple combination vs. 7.8 months exemestane and everolimus alone), the probability of observing a small hazard ratio is sufficiently large. If the true hazard ratio is 1, the probability of observing a small hazard ratio is small enough.

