[Table 7.6: 2](#) summarizes different numbers of PFS events and associated probabilities for observing hazard ratio less than some thresholds under different assumptions of true hazard ratio value. With 90 PFS events, if the true HR is 0.72, the chance of observing a treatment effect with HR of  $\leq 0.8$  is 69%, while the chance of observing a treatment effect with HR of  $\leq 0.9$  is 86%. With 90 PFS events, if the true HR is 1.0, the chance of observing a treatment effect with HR of  $\leq 0.8$  is 14%, while the chance of observing a treatment effect with HR of  $\leq 0.9$  is 31%. In this phase II exploratory study, the sample size is calculated to make an informed decision instead of confirmatory hypothesis testing.

If the PFS events are to be increased from 90 to 100, the probability of observing a treatment effect with HR of  $\leq 0.85$  is increased by 2% (from 78% to 80%) if true HR is 0.72. The same probability is increased by 1% (from 61% to 62%) if true HR is 0.8. Increasing the sample size will benefit more if the true HR is smaller. However, the probability of 78% when true HR is 0.72 is considered high enough for 90 PFS events in this exploratory setting.

Proprietary confidential information.

© 2016 Boehringer Ingelheim International GmbH or one or more of its affiliated companies. All rights reserved.

This document may not - in full or in part - be passed on, reproduced, published or otherwise used without prior written permission.

Table 7.6: 2

Number of PFS events and corresponding probability of making observing HR below thresholds

		Probability  observing HR of $\leq$			
PFS Events	True HR	0.8	0.85	0.9	1.0
80	0.72	68%	77%	84%	93%
90		69%	78%	86%	94%
100		70%	80%	87%	95%
		Probability  observing HR of $\leq$			
PFS Events	True HR	0.8	0.85	0.9	1.0
80	0.80	50%	61%	70%	84%
90		50%	61%	71%	86%
100		50%	62%	72%	87%
		Probability  observing HR of $\leq$			
PFS Events	True HR	0.7	0.8	0.85	0.9
80	1.0	6%	16%	23%	32%
90		5%	14%	22%	31%
100		4%	13%	21%	30%

 Calculated based on the approximate normal distribution of the estimated log HR.

Ninety PFS events is considered sufficient in this phase II trial to show positive efficacy signal if the experimental treatment is superior to the control.

Assuming constant recruitment rate of 12.5 patients per month for a period of A months, the percentage of observed PFS events relative to sample size is a function of study duration T:

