7 PLANNED ANALYSES

The labelling and display format of statistical parameters will follow BI standards [\(7\)](#).

Unless otherwise specified, outputs will be displayed separately for each part of the trial.

Descriptive statistics for continuous variables will generally contain N (number of patients in that patient set with non-missing values), Mean, Standard Deviation, Minimum (Min), 25th percentile (Q1), Median, 75th percentile (Q3), Maximum (Max). In general, means, standard deviations, medians, Q1 and Q3 will be presented to one more decimal place than the raw data. Minima and maxima will be presented to the same number of decimal places as the raw data.

For time-to-event analysis tables, the set of statistics is: number of patients [N (%)], Number of patients with event [N (%)], Number of patients censored [N (%)], <Time to event> [months] followed by Q1 (25th percentile), Median, Q3 (75th percentile). If not specified otherwise, the duration as well as time to event will be displayed in months.

Tabulations of frequencies for categorical data will include all possible categories and will display the number of observations in a category as well as the percentage (%) relative to the respective treatment group total. Percentages will be rounded to one decimal place.

In general a category “missing” will be displayed, if there are missing data for the corresponding variable. Percentages will also generally be based on all patients in the respective patient set whether they have non-missing values or not.

The primary analysis will include all treated (Phase Ib) or randomised patients (Phase II), following the ITT approach (as specified in [Section 6.3](#)).

The analyses for the primary endpoint of PFS as well as best overall response, OR, time to OR, duration of OR, DC, duration of DC, time to progression, tumor shrinkage, tumor size as well as the [REDACTED] will be based on data obtained until November 25th 2016. A sensitivity analysis for the primary endpoints PFS will be performed using all data. Analyses of other RECIST based endpoints will also only utilise data obtained from assessments scheduled until November 25th 2016. For overall survival all available data will be used.

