7.8.1 Adverse events

The analyses of AEs will be descriptive in nature. All analyses will be based on the number of patients with AEs (not the number of AEs).

Proprietary confidential information © 2018 Boehringer Ingelheim International GmbH or one or more of its affiliated companies

For analysis multiple AE occurrence data on the CRF will be collapsed into an AE event provided that all of the following applies:

- All AE attributes are identical (Lowest Level Term (LLT), Common Terminology Criteria for Adverse Events (CTCAE) grade, action taken with trial medication, therapy required, seriousness, reason for seriousness, relationship, outcome, AE of special interest)
- The occurrences were time-overlapping or time-adjacent (time-adjacency of 2 occurrences is given if the second occurrence started on the same day or on the day after the end of the first occurrence)

For further details on summarisation of AE data, please refer to [\(2\)](#) and [\(4\)](#).

Adverse events will be coded with the most recent version of MedDRA. The severity of AEs will be scaled according to CTCAE (CTCAE version 4.03 ([R10-4848](#))).

The analyses of AEs will be based on the concept of treatment-emergent AEs. For the phase Ib, that means that all AEs with an onset between first treatment administration until end of the REP will be assigned as 'on treatment'. All adverse events occurring before first drug intake will be assigned to 'screening' and all adverse events occurring after the REP will be assigned to 'post-treatment'; these AEs will be displayed in separate tables and listings. First drug intake includes the run-in period for Phase Ib part.

For the phase II part it has to be taken into consideration that the sponsor decided to stop treatment with xentuzumab on 28th of October 2016, but continued treatment with everolimus and exemestane. Therefore, the analysis of on-treatment AEs will be split in two parts:

1) AEs with onset date on or before 9th of December 2016

This includes the following patients:

- Patients of both arms who completed the REP on or before 9th of December 2016, i.e. AEs until the end of REP will be considered.
- Patients who stopped xentuzumab on 28th of October 2016 due to sponsor's decision, i.e. AEs with onset date on or before the 9th of December 2016 will be considered.
- Patients receiving everolimus and exemestane only, i.e. AEs with onset date on or before 9th of December 2016 will be considered.

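### The Phase II safety comparison uses crude percentages of patients with AEs although time at risk can differ by arm; the distortion is modest, and cumulative incidence at fixed times would largely remove it

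*Protocol*

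**What the plan says.** Protocol 7.3 commits to a comparison of safety between the arms: "The safety profile of the Phase II part will be compared in a descriptive manner between the experimental and the control arm". The method is in the SAP. Section 7.8.1 makes the patient the counting unit: "All analyses will be based on the number of patients with AEs (not the number of AEs". Section 7 shows each category as a number "as well as the percentage (%) relative to the respective treatment group total". For Phase II, section 7.8.1 tabulates these by treatment, in one part for onset up to 9 December 2016 and another for later onset.

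The length of observation is tied to treatment. The synopsis gives the duration as "Continuous treatment until disease progression, intolerable AEs, consent withdrawal or non-compliance with the study protocol", and protocol 3.1 adds: "Continued treatment beyond disease progression will not be allowed in the study". SAP 6.1 counts data as on-treatment through a residual effect period (REP) of 42 days. Treatment duration and dose intensity are defined in SAP 5.4.2 and summarised by treatment group under SAP 7.7, apart from the AE tables. The visible text contains no AE rate per patient-time, time to first AE, cumulative incidence or fixed-window AE comparison.

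**The concern.** A crude percentage combines two things: how fast AEs arise and how long patients are watched. When treatment ends at progression or intolerance, the second can differ between arms for reasons unrelated to toxicity. An arm that delays progression accumulates more patients with at least one AE at the same underlying hazard. An arm whose patients stop sooner shows fewer, and a real excess can be hidden. The common calendar cut-off limits the difference but does not remove it, because patients who progress still leave the risk window earlier.

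The question has content here. Protocol 2.3 raises the possibility that the antibody aggravates everolimus toxicity, naming mucositis and metabolic disturbance. In this trial the two-arm comparison is the direct evidence on that, and SAP 4.2 says the report is to document the results for future trials.

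**Working it through.** **Inputs.** Protocol 7.6 sizes the trial on "median PFS 10.8 months of triple combination vs. 7.8 months exemestane and everolimus alone", and on recruitment described as: "Assuming constant recruitment rate of 12.5 patients per month for a period of A months", with A = 12 in Table 7.6: 3. The planned readout in protocol 7.3.1 was: "The primary analysis of PFS will be conducted and reported when approximately 90 patients (out of 150 randomized patients) have progressed or died". The REP is ρ = 42 days = 1.38 months. The documents give no AE hazard, no treatment duration by arm and no date of first randomisation, so these are assumed below.

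**Reproducing the plan's own figures.** With exponential PFS, λ = ln 2 / median gives 0.0642 (Arm 2) and 0.0889 (Arm 1) per month. Solving 150 × (1 − c) × F(T) = 90, with the protocol's formula for F(T), gives T = 24.90, 27.93 and 32.54 months for c = 20, 25 and 30%; the protocol states 24.9, 27.9 and 32.5. For 90 events, Φ[(ln 0.8 − ln HR) / (2/√90)] gives 69.1% at HR 0.72 and 14.5% at HR 1; the protocol states 69% and 14%.

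**Time on treatment, if it equals PFS.** Without a cut-off the means are 1/0.0642 = 15.6 and 1/0.0889 = 11.3 months (ratio 1.38). At a 24.9-month readout they are 10.83 and 9.05 months (1.20). Under the 9 December 2016 cut-off, with first randomisation 12 to 20 months earlier and recruitment ending 42 days before it, the ratio is 1.09 to 1.14.

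**Crude percentage at an identical AE hazard r in both arms.** With no cut-off and no REP it is r/(r + λ). If Arm 1 shows 30%, then r = 0.3 × 0.0889 / 0.7 = 0.0381, and Arm 2 shows 0.0381 / (0.0381 + 0.0642) = 37.2%. With the REP and a cut-off, a patient with available follow-up F > ρ stays AE-free with probability

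e^(−rρ) · λ/(λ + r) · [1 − e^(−(λ+r)(F−ρ))] + e^(−λ(F−ρ)) · e^(−rF),

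averaged over uniform entry. Solving for the r that gives the Arm 1 percentage, then applying it to Arm 2:

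| Scenario | Arm 1 10% | Arm 1 30% | Arm 1 50% |
|---|---|---|---|
| No cut-off, no REP | 13.3% | 37.2% | 58.1% |
| Readout at 24.9 months | 11.5% | 34.0% | 55.4% |
| Readout at 30 months | 11.8% | 34.7% | 56.2% |
| 9 Dec 2016, first randomised 12 months earlier | 10.6% | 31.4% | 51.9% |
| 9 Dec 2016, 16 months earlier | 10.8% | 32.0% | 52.6% |
| 9 Dec 2016, 20 months earlier | 11.0% | 32.5% | 53.2% |

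At fixed hazards of 0.05 and 0.10 per month and a cut-off at 26 to 30 months, Arm 2 against Arm 1 is 42–44% against 37–39% and 63–64% against 57–58%, an excess of 5 to 6 points.

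**Opposite direction.** If Arm 2 stops at 1.3 times the control hazard, the same r gives 0.0381 / (0.0381 + 1.3 × 0.0889) = 24.8% against 30%, with no cut-off.

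**Early-onset AEs.** If the hazard exists only in the first 2 months, the crude percentage without REP or cut-off is r/(r + λ) · [1 − e^(−2(r+λ))], and 30% in Arm 1 becomes 30.7% in Arm 2.

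**Precision.** With 75 per arm the 95% half-width of a difference is 1.96 × √(2p(1 − p)/75): 14.7 points at p = 0.3 and 16.0 at p = 0.5.

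**Comparing remedies.** For AEs of equal incidence confined to the first 1 to 3 months, a first-event rate per patient-month gives a false rate ratio of 0.93–0.96 at an assumed early cut-off and 0.84–0.88 at 26–30 months. Cumulative incidence at fixed times was equal in both arms under constant and early hazards alike. At r = 0.10, for example, it is 1 − e^(−0.3) = 25.9% at 3 months and 1 − e^(−0.6) = 45.1% at 6 months in each arm.

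**The case against.** The strongest reply is that the effect is small and the analysis exploratory. Protocol 7.1 plans no formal testing, and crude patient incidence is a legitimate description. Under the cut-off that now applies, the distortion lies far inside sampling error. That stands and limits how much weight the point can bear, but it does not justify leaving out a simple check on a systematic error.

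A reader might infer that the plan itself expects longer treatment in Arm 2, so that Arm 2 is bound to look more toxic. The documents do not support this. Protocol 7.6 states HR 0.72 as a condition and also considers HR 1. No treatment duration is stated, and stopping for intolerance could reverse the direction. A reader might also take 5 to 6 points as the expected error; that belongs to a 26–30 month readout that SAP 7.8.1 replaces with 9 December 2016.

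Other limits stand. Equating time on treatment with PFS ignores other reasons for stopping: an assumed extra stop hazard of 0.03 per month in both arms lowers the planned-readout excess to about 3.6–4.8 points and leaves 1.4–2.0 at the early cut-off. The documents give no AE onset times, so which AEs keep arising is unknown. The exposure tables, and the start and end days in the AE listings, let a reader see an imbalance in duration, though they do not correct the percentages. The company AE standards, the project safety SAP and protocol amendment 3, all cited in the SAP, were not available, so it cannot be said that no such analysis exists anywhere.

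**Conclusion.** The point holds in a limited form. The visible plan compares safety between arms on percentages that do not allow for time at risk, and time at risk can differ by arm. For AEs that keep arising, the expected distortion under the 9 December 2016 cut-off is about 1 to 3 points (0.6 to 3.2 for Arm 1 percentages of 10 to 50%), against a half-width of about 15 points if 75 patients per arm are enrolled. Because recruitment was stopped early, the number may be lower and the interval wider.

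The figure assumes exponential PFS with the sizing medians, treatment ending at progression, a constant AE hazard equal in both arms, and first randomisation 12 to 20 months before the cut-off. The direction is conditional: an apparent excess in Arm 2 if it is treated longer, a masked excess if it stops sooner, and almost nothing for AEs confined to the first one or two months. The sentence in protocol 7.3 is not itself in error; the gap is in the SAP's choice of measure.

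**What to change.** In SAP 7.8.1, for the Phase II tables of overall AEs, AEs of grade 3 or higher, SAEs and the user-defined AE categories, add by arm the cumulative incidence of first event at fixed times, such as 3 and 6 months from first dose, with 95% CI. End follow-up at the end of the REP or on 9 December 2016, whichever is earlier, as censoring, and treat death as a competing event. Read the between-arm safety comparison from these figures alongside the crude tables and the SAP 7.7 exposure summary.

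A first-event rate per patient-month may be added as a supplement, but should not carry the safety statement, because it makes the longer-treated arm look safer for early-onset AEs.

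The cost is a few extra tables from dates already collected. Intervals will be wide at later times. The estimate also assumes that patients whose risk window closes had the same AE risk as those still observed, which the report should say.
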